Despite awareness in the celiac community of the potential for pancreatic exocrine insufficiency as a complication of celiac disease, there have been few prospective studies of pancreatic enzyme replacement in celiac disease and no studies to date that have taken place in the United States. As the population with celiac disease has expanded rapidly in recent years, 30 the potential for adjunctive therapies for celiac disease has become more apparent. In this study, we propose to conduct a rigorous prospective study of the utility of pancreatic enzyme replacement in celiac disease and assess the ability of fecal elastase levels to predict response to therapy.

Our goal is to provide adequate supplementation over the 10 day treatment period so as to maximize the opportunity for an evident therapeutic effect if indeed pancreatic enzyme insufficiency is contributing to the subjects' symptoms.

B3. DESCRIPTION OF RESEARCH PROTOCOL

A. Study Design – Overview, Methods, Procedures

Overview

This is a single-center investigator initiated phase IV trial to examine the efficacy of pancreatic enzyme supplementation in individuals with celiac disease who suffer persistent symptoms despite a gluten free diet.

Hypothesis

Pancreatic enzyme supplementation will improve symptoms in individuals with celiac disease who suffer persistent symptoms despite a gluten free diet.

Specific Aims:

Specific Aim 1: Evaluate the efficacy of pancreatic enzyme supplementation for reduction of gastrointestinal symptoms in patients with celiac disease on a gluten free diet.

Specific Aim 2: Assess the ability of fecal elastase levels to predict response to pancreatic enzyme supplementation in patients with celiac disease on a gluten free diet.

Primary Objective(s)/End Point(s):

The primary endpoint for Specific Aim 1 will be the average per individual subject on-treatment score in the Celiac Disease Gastrointestinal Symptom Rating Scale (CeD GSRS) domains of Diarrhea, Indigestion, and Abdominal pain comparing active treatment to placebo (i.e. a paired comparison of CeD GSRRS on treatment versus on placebo for each subject). The outcome measures used in the study and in particular the CeD GSRS have been employed previously by the investigators in their published studies. 31-33

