Supplemental information shall be submitted as soon as available and may include laboratory results, radiology reports, progress notes, hospital admission and emergency room notes, holding and observation notes, discharge summaries, autopsy reports, and death certificates.

Regarding the reporting of pregnancy: Study center personnel will report every pregnancy on a pregnancy report form as soon as possible (within 24 hours of first awareness of the pregnancy to the pregnancy fax number, [name]), even if no AE has occurred, and follow it to term. If, however, the pregnancy is associated with an SAE (e.g. if the mother is hospitalized for dehydration), in addition to the pregnancy report form, a separate SAE report form will be filed.

All relevant SAE or pregnancy information will be faxed to the Forest Global Drug Safety Department at **[contact]**.

B. Statistical Considerations

Sample Size Justification:

As this is a pilot study and the response of celiac symptoms to pancreatic enzyme supplementation has never been assessed, sample size is not possible to definitively calculate. However, based on the literature, a standard deviation of σ =0·55 is estimated and a >0.4 point change in CeD-GSRS can be considered clinically significant. Allowing for a type-1 error rate of α =0·05, and assuming a 10% drop-out rate, 32 total participants would provide 80% power to detect a 0·4-point difference in CeD-GSRS score between pancreatic enzyme treatment and placebo using a two treatment cross over design. Allowing for drop out and treatment non-compliance we plan to recruit until 30 participants have completed the treatment phases, up to a maximum of 40 eligible individuals. While this may appear somewhat overpowered, this sample size is feasible and allows for what is a very high degree of uncertainty regarding both the possible treatment effect and the influence of fecal elastase levels on efficacy, as described below.

Data Analysis:

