Efficacy analyses will include all patients receiving ≥1 dose of study drug during double-blind treatment and with ≥1 post-baseline assessment (Modified Intent-to-Treat [MITT] population). Baseline score will be considered the last non-missing observation before the first dose of pancreatic enzyme or placebo. The primary endpoint is the difference in mean CeD-GSRS score on treatment vs. placebo. Mean score for each participant will be generated by averaging the daily patient reported outcome (CeD-GSRS and CSI) scores across the study periods, such that there will be a single mean score per participant for the run-in phase and each treatment phase. The mean intrasubject score will then be averaged across the entire cohort for the relevant study phase.

We will use standard two-treatment cross over study analysis in which participant scores during drug treatment (GSRS_{rx}) for the primary outcome are compared to participant scores on placebo (GSRS_{pcb}). Assuming the data are normally distributed, if pancreatic enzyme supplementation is effective we would expect GSRS_{rx} < GSRS_{pcb}. The study as describe above is powered so that we will reach statistical significance if GSRS_{pcb} - GSRS_{rx} >0.4 using Student's paired t-test p<0.05.

Sensitivity analyses will be conducted using Mixed Model for Repeated Measures (MMRM). MMRM analyses will include treatment and study week as main effects, gender, baseline CeD-GSRS score as covariates, and weekly CeD-GSRS scores as repeated measures. Should data be non-normal, we will transform results into categorical data by calculating the proportion of patients with a >30% reduction in CeD-GSRS score on treatment and on placebo compared to their individual scores at baseline. If treatment is effective, we would expect a significantly greater proportion of patients to have a minimally clinically significant difference in GSRS score on treatment compared to placebo which can be evaluated using the Fishers Exact Test.

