A primary secondary outcome will be an assessment of treatment response by fecal elastase status. We will assess the ability of fecal elastase levels to predict response to therapy in two separate analyses. In the first, we will assess the proportion of treatment responders among individuals with low fecal elastase defined as levels less than 100, compared to those with fecal elastase levels greater than 100. This proportion will be compared using Fisher's exact test. Separately, as we cannot reliably predict the spectrum of fecal elastase levels or the degree of improvement with therapy we will evaluate any correlation between fecal elastase levels and change in CeD-GSRS scores both in univariate analysis and after controlling for demographics and relevant clinical variables including time on the gluten free diet.

Further secondary outcomes will include mean CSI scores on treatment vs. placebo, as well as difference between mean run-in CeD-GSRS and CSI scores and mean scores on treatment vs. placebo, and the proportion of patients achieving a 50% reduction in mean abdominal pain score from baseline with drug vs. placebo. Secondary endpoints will be analyzed similarly to the primary endpoint using Student's T test for normally distributed continuous variables and fishers exact test for non-normal or categorical variables.

All descriptive data, including participant demographics, will be presented as the mean and 95% confidence interval.

All statistical tests will be analyzed with SPSS software (version 19; SPSS Software, Microsoft Corp., Redmond, WA, USA). A *P* value of .05 or less will be considered statistically significant.

Safety assessments will performed for all patients who received ≥1 dose of pancreatic enzyme or placebo.

C. Subject Selection

Inclusion Criteria:

- 1. Biopsy proven celiac disease.
- 2. Age 18-80.
- 3. Ongoing symptoms defined as a CeD-GSRS score in the highest domain of 3 or greater at Visit 1.
- 4. Subject must be following a gluten free diet.
- 5. tTG < 40 units at screening.

Exclusion Criteria:

- 1. Taking prescription or over the counter enzyme supplements for 1 month prior to enrollment.
- 2. Pregnant, breastfeeding or planning pregnancy. Woman using acceptable methods of contraception will be included. Acceptable methods of contraception include oral hormonal contraceptives, implanted hormonal contraceptives, diaphragm with spermicide, condoms, intra-uterine device, abstinence, and male partner vasectomy.

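### The only stand-alone abdominal-pain outcome is a 50%-reduction proportion, which would usually miss a 0.4-point shift in pain; the continuous score is already collected and should be compared directly

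*Combined protocol and SAP*

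**What the plan says.** Section B3.B, Data Analysis, ends its list of further secondary outcomes with "the proportion of patients achieving a 50% reduction in mean abdominal pain score from baseline with drug vs. placebo". Secondary endpoints are to be analysed with a t-test if continuous and normal, and with "fishers exact test for non-normal or categorical variables" otherwise, so this proportion goes to Fisher's test. The section does not say which instrument supplies the pain score, and gives no reason for the 50% cut.

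Abdominal pain also enters the primary endpoint. Section B3.A, Primary Objective(s)/End Point(s), uses the CeD-GSRS "domains of Diarrhea, Indigestion, and Abdominal pain comparing active treatment to placebo", as a within-subject comparison, which Data Analysis tests "using Student's paired t-test p<0.05". No section plans a separate enzyme-versus-placebo comparison of the pain score itself.

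Under Number and Timing of Visits/Evaluations, the CeD-GSRS is completed at the end of each phase (days 7, 17, 24 and 34). Each completer therefore has a score at the end of both treatment periods.

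The Sample Size Justification says that "a standard deviation of σ =0·55 is estimated and a >0.4 point change in CeD-GSRS can be considered clinically significant", and that "we plan to recruit until 30 participants have completed the treatment phases, up to a maximum of 40 eligible individuals".

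**The concern.** A score that exists for every completer under both treatments is reduced to a yes/no before the treatments are compared. The cut is far from the effect that the plan regards as meaningful. At a baseline of 3, a 50% fall is 1.5 points, which is 1.5/0.4 = 3.75 times the 0.4-point difference. A shift of 0.4 carries few patients across such a line.

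Pain is one of the three symptoms that make up the primary question, and the three-domain average cannot show whether pain itself improved. What is at stake is the one result that speaks to pain alone. A non-significant responder comparison could be read as absence of an effect on pain when it had little chance of showing one. In a pilot, a paired mean difference with its interval would also be more useful for planning later work.

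**Working it through.** **Inputs from the documents.** Difference 0.4, SD 0.55, alpha 0.05, 30 completers. The plan does not state sidedness; two-sided is assumed.

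**Reproducing the plan's figure.** The plan states that "Allowing for a type-1 error rate of α =0·05, and assuming a 10% drop-out rate, 32 total participants would provide 80% power". Reading 0.55 as the within-subject SD per period, the SD of a paired difference is 0.55 × √2 = 0.778. For n = 32 the noncentrality is 0.4/(0.778/√32) = 2.91, and the noncentral t gives 80.5% power. So 32 reproduces as an evaluable number. Reading 0.55 as the SD of the difference needs only 17 by the t-test, so it does not reproduce. The first reading is used below.

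**Paired t-test on the pain score, 30 completers, no floor.**
- SD 0.55: 0.4/(0.778/√30) = 2.82, power 78%.
- SD 0.8: 0.4/(1.131/√30) = 1.94, power 46%.
- SD 0.95: 0.4/(1.344/√30) = 1.63, power 35%.

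The value 0.95 is 0.55 × √3, the single-domain SD if the errors of the three domains were independent and equal.

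**What the responder test needs.** With 30 per condition and no responders on placebo, Fisher's test needs 6 on enzyme (6 v 0, p = 0.024; 5 v 0, p = 0.052). Exact McNemar also needs 6 discordant patients, all in one direction (2 × 0.5⁶ = 0.031; with five, 0.0625).

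**Simulation.** Each patient's true mean is normal. Baseline, placebo and enzyme scores each add independent error. The placebo score is lowered by the placebo response, and the enzyme score by that plus 0.4. A responder has a score at or below half of baseline. Assumptions not in the documents: mean baseline pain 2.5–4, between-patient SD 0.5–1.0, placebo response 0–1.0 points, no carryover or period effect. A scale floor of 1 is tried as a variant. Ranges run over all combinations and are subject to simulation error of a point or two.

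| Per-period SD | Floor at 1 | Fisher | Exact McNemar | Paired t on score | Smallest gain over McNemar |
|---|---|---|---|---|---|
| 0.55 | no | 0–34% | 0–41% | 76–79% | about 37 points |
| 0.55 | yes | 0–26% | 0–33% | 60–79% | about 38 points |
| 0.8 | no | 0–19% | 0–22% | 45–48% | about 25 points |
| 0.8 | yes | 0–13% | 0–17% | 34–47% | about 24 points |
| 0.95 | no | 1–12% | 1–15% | 34–37% | about 19 points |
| 0.95 | yes | 0–9% | 1–12% | 26–36% | about 18 points |

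**One case in full** (baseline 3, between-patient SD 0.5, per-period SD 0.55, no floor). With a placebo response of 0.5, responders are 18% on enzyme and 7% on placebo; power is 12% (Fisher), 14% (McNemar) and about 78% (paired t). With no placebo response, responders are 5% v 1% and Fisher's power is near zero. With a 1.0-point placebo response they are 44% v 22%, and Fisher reaches 31%.

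**Other reading of 0.55.** If it were the SD of the difference (no floor), the paired t would have 96–98%, McNemar 0–69% and Fisher 0–60%, with a smallest gain over McNemar of 28 points.

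**The case against.** A reader might infer that pain is analysed nowhere else, or that the trial would miss the effect it is built for. The documents support neither. Pain is a component of the continuous paired primary endpoint, and the 0.4-point design difference belongs to that endpoint, which keeps its power. Nor can one say that the responder test almost always fails. That fits no or moderate placebo response, but with low baseline pain and a 1-point placebo response Fisher's power reaches about a third at SD 0.55.

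Four further objections have weight.
- The 0.4 and 0.55 are given for CeD-GSRS. One domain is probably noisier than an average of three; at SD 0.95 the paired t-test would itself miss the effect about two times in three. This stands, and is why a range is shown. The advantage of the score narrows but does not vanish.
- The instrument behind the pain score is not named. If it is not the CeD-GSRS, the figures above do not carry over. This stands, and the fix settles it.
- A 50% responder rate asks how many patients gain a large benefit, which a mean does not answer. This is a reason to keep the proportion, but not to make it the only test of pain.
- The stakes are modest. This is a pilot, the formal list under Secondary Objective(s)/End Point(s) omits pain, and nothing says a non-significant result would be reported as no effect. This limits the priority of the change.

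The loss is not just a matter of Fisher's test ignoring the pairing: it persists under exact McNemar.

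**Conclusion.** The point holds for the stand-alone pain outcome only. For a 0.4-point shift in the pain domain with 30 completers, the planned comparison would usually miss it, with power of at most about 34% at the SD reading that reproduces the plan's 32 and at most about 19% if the domain is noisier. Comparing the score directly gains roughly 20 points or more over even a correctly paired responder test, and more over Fisher's test. The size rests on carrying 0.4 and 0.55 over to a single domain and on the assumed baseline, spread and placebo response; the direction was the same in every combination tried. It is a cheap improvement to a secondary outcome and worth making.

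**What to change.** In B3.B, Data Analysis, name the CeD-GSRS abdominal-pain domain as the pain score. Make the outcome the within-patient enzyme-minus-placebo difference, analysed as the primary endpoint is: paired mean difference with 95% CI. State that the comparison stays on the score even if its distribution looks non-normal, since the plan's rule would otherwise turn it back into a proportion. Keep the 50%-reduction proportion, by treatment, as a supportive descriptive figure.

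The cost is a few sentences. No visits, questionnaires or patients are added, and the number of tests does not rise because one replaces another. The small downside is that the responder proportion loses its own significance test.

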
[figure not shown]

(Screening)

Visit 1

Medical Hx

Protocol Appendix A

Total duration of study medication administration = 34 days
Omeprazole co-prescribed for entire duration of study
Phone Contacts every 3 +/- 1 days

Daily stool consistency log & Daily medication log Daily CSI questionnaire & Weekly CSI and CeD-GSRS Questionnaires

*Phase 1 will begin once the subject's safety and celiac serologies have returned and been evaluated by a study physician. At that point the subject will be instructed to begin taking the study medication and to begin completing the daily and weekly questionnaires.
